45 criteria of established regulatory standards is proposed for Inova Health Systems.

1 **Safety Considerations:**

2 1) Clinical use of convalescent plasma in this setting is regarded as investigational
3 as the safety and efficacy of convalescent plasma are unproven in the setting of this novel
4 pandemic. Collection and clinical use of this product will be managed as an experimental therapy
5 consistent with ethical safeguards (informed consent of donors and recipients, FDA approval
6 through IND pathway, institutional approval, and special labeling).

7 2) Procedures will maximize safety of both plasma donors and recipients.

8 a. Standard blood donation protocols and screening will be followed (Donor History
9 Questionnaire, Appendix E)

10 b. Potential donors will be assessed by physician or nurse practitioner to assure clinical
11 stability and full recovery (confirmed by nucleic acid amplification technology (NAT))
12 prior to donation

13 c. Plasma collections must be separated by \geq 28 days, eligibility must be re-evaluated at each
14 collection, and total volume collected will be based on estimated donor blood volume in
15 accordance to guidelines for healthy donors

16 d. As with other plasma therapies, ABO compatibility will be assured

17

18

19 e. Potential risks to convalescent plasma recipients will be discussed in the informed consent
20 process and monitored for closely in the hospital setting:

21 i. risk of unintended transmission of relevant transfusion transmitted diseases from
22 donor

23 ii. risks of transfusion related reactions

24 iii. theoretical risk of immune enhancement due to transferred antibodies that could
25 exacerbate the disease

26

27

28

29

30

31

32

33

34

35

36

37

1 Plasma Collection and Storage: Collection, storage, and preparation of plasma will be performed by the
2 Inova Blood Center Staff. The plasma product is to be handled like a regular or licensed FFP/FP24, with
3 special labeling. Convalescent plasma will be stored at the Inova Blood Donor Services Facility, the
4 largest hospital based donor center in the country. It is a well-established and regulated BSL2 facility
5 which is CLIA/CAP certified in full compliance with regulatory guidelines including AABB, FDA, with
6 use of good manufacturing practices.

7 The Inova Blood Center Staff are routinely engaged in automated plasma collection and preparation in

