8 accordance with American Association of Blood Banks (AABB) and FDA guidelines 21 CFR Part 640
9 Standard Operating Procedures¹⁷. For automated plasma collection instruments, the allowable volume of
10 collection is predetermined based on a set of parameters as approved by FDA.

11

1 All established safeguards for prevention of relevant transfusion transmitted diseases for standard blood
2 donation will be followed. Infectious disease testing includes EIA(enzyme immunoassay): HTLV 1 and 2;
3 Syphilis; HIV 1, 2 and group O, Hepatitis B, Hepatitis C, Trypanosoma cruzi. Nucleic acid tests (NAT)
4 are performed for: HIV 1 and 2, Hepatitis B, Hepatitis C, West Nile Virus and Zika. Other tests include
5 antibody screen and ABO-Rh, all in accordance with FDA regulatory standards. In addition, Babesia was
6 recently identified by FDA as a relevant transfusion transmitted disease. Therefore, Babesia testing will be
7 implemented as soon as feasible no later than May 31, 2020 by Inova Blood Center.

8 Convalescent plasma will be collected from a single donor connected to an apheresis equipment (TRIMA
9 by Terumo-BCT) using an anticoagulant: ACD-; frozen within 8 hours; volume: 200 – 600ml and may be
10 separated into 200 ml aliquots and stored: < -18°C with a shelf-life of 365 days.

11 Plasma units will be labeled in the standard manner with ABO typing but will also include the following
12 statement, "*Caution: New Drug--Limited by Federal (or United States) law to investigational use.*" (21
13 CFR 312.6 (a)).

14

15

16

17

18

19

20

21

22

23

24

25

1 **Structure of Study:**

2 **Phase 1:**

3 Phase 1 will be recruitment and enrollment of plasma donors.

4 **Phase 2:**

5 Phase 2 will be continued recruitment and enrollment of plasma donors, with the addition of recruitment
6 and enrollment of plasma recipients.

7 **Study Participants:**

8 **PLASMA DONORS:**

9 **Inclusion Criteria for Convalescent Plasma Donors:**

10 Outpatients 18 years old and older who have recovered from COVID-19:

11

- 12 • Have proof of Original Positive SARS-CoV-2 NAT nasopharyngeal (NP) test result
- 13 • Complete resolution of symptoms at least 14 days prior to donation
- 14 • Negative SARS-CoV-2 NAT nasopharyngeal (NP) specimen at screening visit
- 15 • Able to meet standard criteria for blood donation
- 16 • Clinically stable based on provider assessment

17 **Recruitment Population:** Self- referrals from community with local advertisement tools utilized. Patients

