4 will be performed to permit retrospective determination of the characteristics of an effective product and
5 dosage regimen, and the characteristics of patients most likely to benefit¹⁸.

6 Data and blood specimen will be banked for future use pursuant to the IRB Approved Inova COVID-19
7 Biobanking Protocol. We will follow the guidelines and procedures for specimen storage and access as
8 described in the IRB approved Inova COVID-19 Biobanking Protocol.

9 Specimens will be stored at the Office of Research at Inova Biobank with standard certifications in place.

10

1 **PLASMA RECIPIENTS:**

2 **Inclusion Criteria for Recipients of COVID-19 Convalescent Plasma:**

3 Patients in the Inova Health System with confirmed COVID-19 by PCR testing

4 Age \geq 13 years

5 Currently hospitalized with COVID-19 infection with severe or life-threatening clinical syndrome²² as
6 follows:

7 Severe COVID-19: (three or more of the following)

8

- 10 • Dyspnea
- 11 • Respiratory rate \geq 30/min
- 12 • Blood oxygen saturation (SpO₂) \leq 94% on room air
- 13 • Partial pressure of arterial oxygen to fraction of inspired oxygen (P:F) ratio $<$ 300
- 14 • Pulmonary infiltrates $>$ 50% of lung parenchyma within 24 to 48 hours

15 Life-threatening disease is defined as: (one of the following)

- 16 • Respiratory failure
- 17 • Septic shock, and/or
- 18 • Multiple organ dysfunction or failure

19 Patient must provide informed consent or have health care power of attorney/next of kin provide consent
20 if he/she cannot.

21 **Exclusion Criteria:**

22 Contraindication to receive plasma as deemed by the treating physician

23 Severe hypercoagulable state (documented in medical chart or by treating physician assessment)

24 Absolute IgA deficiency

25 Prior history of Transfusion Related Acute Lung Injury (TRALI)

26 Inability to tolerate plasma volume due to severe systolic or diastolic heart failure despite slower infusion
27 and diuretic administration

28 Positive pregnancy test (HCG)

29 **Recipient Screening Labs**

30 Blood Type

31 Total immunoglobulin (Ig) levels: IgG, IgA, IgM

32 Coagulation tests to include PT/INR and PTT

33 Complete blood count and differential

34 **Pre-Treatment Testing:**

35 Optional Blood draw for Inova COVID-19 Biobank (up to four tubes each) prior to each dose of plasma

36 **Target Recipient Recruitment:** 150-200 individuals

37 **Primary Endpoints:**

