38 1) Change in clinical status as captured by 7-point ordinal scale score (being utilized in Gilead Sciences
39 remdesivir trial^{19, 20}) at time of plasma infusion (day 0) compared to day 7:

40

- 44 1. Death
- 45 2. Hospitalized, requiring mechanical ventilation or ECMO

- 1 3. Hospitalized, requiring non-invasive ventilation or high flow oxygen
- 2 4. Hospitalized, requiring supplemental oxygen
- 3 5. Hospitalized, not requiring supplemental oxygen--requiring ongoing medical care
- 4 (COVID-19 related or otherwise)
- 5 6. Hospitalized, not requiring supplemental oxygen-not requiring ongoing medical care
- 6 (COVID-19 related or otherwise).
- 7 7. Not Hospitalized

8 2) Adverse events related to plasma infusion (within 6 hours of infusion) to include²³:

- 9 a) Transfusion-related events
 - 10 i. Transfusion Associated Circulatory Overload
 - 11 ii. Transfusion-Related Lung Injury
 - 12 iii. Allergic Reaction/Anaphylaxis
 - 13 iv. Transmission of transfusion transmitted diseases
 - 14 v. Febrile Transfusion Non-hemolytic Transfusion Reaction

15 Secondary Endpoints:

- 16 3) Change in 7-point ordinal scale score (being utilized in Gilead Sciences remdesivir trial) from time
- 17 of plasma infusion (day 0-prior to first infusion) to days 14, 21, and 28^{19,20}.
- 18 4) SOFA score at days 0, 7, 14, 21, 28²¹
- 19 5) Time to discontinuation of supplemental oxygen
- 20 6) Duration of hospitalization
- 21 7) Time to liberation from mechanical ventilation (for patients on a ventilator)
- 22 8) Need for mechanical ventilation (For those not on the ventilator)
- 23 9) All-cause Mortality [at 28 days]

24 ○

| Organ System, Measurement | SOFA Score | | | | |
|--|------------|-------------------|--|--|---|
| | 0 | 1 | 2 | 3 | 4 |
| Respiration PaO ₂ /FiO ₂ , mmHg | Normal | <400 | <300 | <200 (with respiratory support) | <100 (with respiratory support) |
| Coagulation Platelets x10 ³ /mm ³ | Normal | <150 | <100 | <50 | <20 |
| Liver Bilirubin, mg/dL (μmol/l) | Normal | 1.2-1.9 (20-32) | 2.0-5.9 (33-101) | 6.0-11.9 (102-204) | >12.0 (<204) |
| Cardiovascular Hypotension | Normal | MAP<70 mmHg | Dopamine ≤5 or dobutamine (any dose)** | Dopamine >5 or epinephrine ≤0.1 or norepinephrine ≤0.1 | Dopamine >15 or epinephrine >0.1 or norepinephrine >0.1 |
| Central Nervous System Glasgow Coma Score | Normal | 13-14 | 10-12 | 6-9 | <6 |

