21 transformations explored as needed. All analyses will be conducted using SAS (version 9.4, Cary, NC)
22 with p<0.05, two-tailed considered statistically significant.

23
24 Primary efficacy endpoints:

25 1. Gilead 7-point scale – For each time point (day 0 vs. 7), summary clinical status scores will be
26 calculated. Changes in scores will be subsequently assessed via a generalized linear mixed model
27 with clinical status assessed at day 0 vs. 7. A statistically significant increase of ± 2 points in β
28 from day 0 to day 7 will be considered as evidence of efficacy. A mixed model allows for
29 examination and inclusion of the variance-covariance matrix into the model as a result of expected
30 within-subject serial correlation as a result of repeated assessments over time.
31 2. Plasma transfusion related adverse events will be scored as 1+ vs. 0 and will be assessed via Chi-
32 Square test with a hypothesized distribution of expected AE (using the higher incidence estimate):
33 i. Transfusion Associated Circulatory Overload: 1:1,566 to 1:68 plasma units
34 transfused
35 ii. Transfusion-Related Lung Injury: 1:1,200 to 1:190,000
36 iii. Allergic Reaction/Anaphylaxis: 1-3%
37 iv. Febrile Transfusion Non-hemolytic Transfusion Reaction: 0.1-1%

38
39 Secondary endpoints:

40 1. Change in 7-point ordinal scale score and SOFA score over time will be assessed via individual
41 growth models (IGM). Times will be day0, 14, 21, and 28
42 2. Mortality will be assessed via Chi-Square test with a hypothesized current mortality rate of 1-5%
43 (age adjusted).
44 3. Need for mechanical ventilation for those not ventilator at time of plasma infusion will be
45 assessed via Chi-Square test with a currently available published estimates.

1 4. Time to discontinuation of supplemental oxygen, time to liberation from mechanical ventilation,
2 duration of hospitalization will be summarized as median (IQR) or rates and compared to currently
3 available published estimates.
4
5

6 **ADVERSE EVENTS AND TOXICITY MANAGEMENT**

7 **Definitions of Adverse Events and Serious Adverse Events**

9 **Adverse Events (AE)**

10 An AE is any untoward medical occurrence in a clinical study subject administered an investigational
11 product, which does not necessarily have a causal relationship with the treatment. An AE can therefore be
12 any unfavorable and/or unintended sign, symptom, or disease temporally associated with the use of an

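### The primary safety endpoint counts transmitted infection only within 6 hours of infusion, so that component will be effectively zero and uninformative

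*Combined protocol and SAP*

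**What the plan says.** Under Primary Endpoints, item 2 reads "Adverse events related to plasma infusion (within 6 hours of infusion) to include", followed by five transfusion-related events. Four are acute reactions: circulatory overload, lung injury, allergic reaction or anaphylaxis, and febrile reaction. The fifth, item iv, is "Transmission of transfusion transmitted diseases". It has no window of its own there or in the Statistical Plan.

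The Statistical Plan (item 2 under the primary endpoints) begins "Plasma transfusion related adverse events will be scored as 1+ vs. 0 and will be assessed via Chi" and goes on to specify a chi-square test against expected rates, taking the higher published incidence. Rates are listed for the four acute reactions, ending with "Febrile Transfusion Non-hemolytic Transfusion Reaction: 0.1-1" percent. None is listed for transmission. The general rule for all tests is "with p<0.05, two-tailed considered statistically significant". Target recipient recruitment is "150-200 individuals".

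Safety Considerations, item 2(e)(i), names "risk of unintended transmission of relevant transfusion transmitted diseases from" the donor as a recipient risk, to be monitored closely in the hospital setting. Plasma Collection and Storage shows which infections are in view for donors: "donation will be followed. Infectious disease testing includes EIA(enzyme immunoassay): HTLV 1 and 2", then syphilis, HIV, hepatitis B and C and T. cruzi, with nucleic acid tests for HIV, hepatitis B and C, West Nile virus and Zika.

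Two other places deal with the same event and set no time limit. The Safety text lists transmission among the anticipated infusion reactions and says these events will be recorded if present. Secondary Endpoints, item 10, records all other adverse and serious adverse events.

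**The concern.** A 6-hour window suits the four acute reactions. It does not suit an infection that must first become detectable and then be looked for. A transmission recognised on day 10 or day 25 falls outside the primary endpoint by rule, and nothing in the recipient schedule would reveal one inside 6 hours. A zero for this component would reflect the window rather than the product. The protocol describes the safety of convalescent plasma in this setting as unproven and names transmission as a recipient risk, so a primary safety component that cannot register it limits what the trial can say on that question.

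**Working it through.** The documents give no expected transmission rate, power or sample size derivation for this component, so there is no figure to reproduce. The check compares sections and then adds an illustration.

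**1. Could the event be seen within the window?**
- Window: 6 hours (Primary Endpoints, item 2).
- Testing time: the donor screening visit text says that transmissible-disease testing of donor blood may take an additional 1–2 days, or 24–48 hours. 24/6 = 4 and 48/6 = 8, so laboratory time alone is 4 to 8 times the window, before allowing for the time an infection takes to become detectable.
- Baseline: Recipient Screening Labs are blood type, immunoglobulins, coagulation tests and blood count. There is no infection test against which to call an infection new.
- Follow-up: the post-treatment draws on days 7, 14, 21 and 28 are optional and for biobanking. The recipient call script asks about residence, oxygen, urgent or emergency visits and re-hospitalization, but not about infection.

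**2. How much would be counted?** Let p be the true transmission rate per recipient, f the share of transmissions recognisable within 6 hours, and n the number of recipients. The chance of counting at least one is 1 − (1 − p·f)^n. The documents give neither p nor f; both are assumptions, shown over a range.

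| Assumed p | f | n = 150 | n = 200 |
|---|---|---|---|
| 1% | 100% (full detection) | 77.9% | 86.6% |
| 1% | 10% | 13.9% | 18.1% |
| 1% | 5% | 7.2% | 9.5% |
| 1% | 1% | 1.5% | 2.0% |
| 0.1% | 100% (full detection) | 13.9% | 18.1% |
| 0.1% | 5% | 0.75% | 1.0% |
| any | 0% | 0% | 0% |

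For example, with n = 150, p = 0.01 and f = 0.05: 1 − (1 − 0.0005)^150 = 0.072.

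**3. Does it disturb the primary test?** At the higher rates in the Statistical Plan, and assuming independence and one infusion each, the probability of any of the four acute events is 1 − (1 − 1/68)(1 − 1/1200)(1 − 0.03)(1 − 0.01) = 0.0546. That gives 150 × 0.0546 = 8.2 to 200 × 0.0546 = 10.9 expected recipients with an event. Transmission adds nothing to this expected count, because it has no rate, and essentially nothing to the observed count, because of the window. The test of one or more events against none gives essentially the same answer with item iv kept or removed.

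**The case against.** The strongest reply is that late infections are not lost. The Safety text and secondary item 10 have no time limit. For patients discharged within 7 days of dosing, follow-up to day 28 asks about urgent, emergency and repeat hospital care for any reason. Optional stored samples might permit a look-back. This stands: a noticed infection can be recorded as a safety event, and the failure is confined to the primary component. It does not repair that component, because these routes depend on clinical recognition, and because Primary Endpoints item 2 and the Safety text then treat the same event differently.

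The donor-screening list is also not a formal definition of item iv. An infection evident within hours, for instance from a contaminated unit, could be counted. Hence the conclusion is effectively zero, not necessarily zero. That the listed infections would not be recognisable at 6 hours is general reasoning; the documents support it only through the 1–2 day testing time.

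Donor screening may well make transmission rare, and nothing in the documents supports a rate as high as the 1% used for illustration. That is a reason not to present transmission as something the primary endpoint measures.

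A reader might infer three stronger things that the documents do not support:
- That the trial as a whole will report no transmissions whatever happens. The other recording routes contradict this.
- That an always-empty component biases the composite test. Step 3 of the working shows that it does not.
- That the trial will publish a misleading upper confidence bound from zero events in 150–200 recipients. The plan proposes no transmission rate, bound or claim of absence.

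**Conclusion.** The concern holds for the primary endpoint component. The 6-hour rule excludes essentially every transmission of the kind that the protocol screens donors for, no recipient testing is scheduled, and there is no reference rate to test a count against. The component will be effectively zero and says almost nothing about transmission. At an assumed 1% true rate with 5% recognisable by 6 hours, the chance of counting one or more is 7.2–9.5%, against 77.9–86.6% with full detection. With none recognisable it is zero at any true rate. These percentages rest on assumed inputs; the mismatch between event and window does not. The primary test result and the efficacy analysis are not materially affected. What changes is what the trial may conclude about transmission.

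**What to change.** Reconcile Primary Endpoints item 2, Secondary Endpoints item 10, the Safety text and the Statistical Plan as follows.

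1. Remove item iv from the 6-hour primary endpoint, leaving the four acute reactions that have reference rates.
2. Add transmission as a separate safety outcome: any infection recognised or diagnosed in routine care from first infusion to day 28 and judged possibly related to the plasma. Report it descriptively.
3. State with the result that an absence of reports, without recipient testing, does not exclude transmission.

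The cost is wording only, with no new visits or tests. Day 28 is already the protocol's follow-up horizon. The trial gives up any primary claim on transmission, and the new outcome still depends on clinical recognition. Because further doses are allowed up to 14 days after the first, a recipient dosed on day 14 would have only 28 − 14 = 14 days of observation after that dose. The limitation statement should say so.

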| Renal Creatinine, mg/dL (μmol/l) or Urine output | Normal | 1.2-1.9 (110-170) | 2.0-3.4 (171-299) | 3.5-4.9 (300-440) or <500 mL/day | >5.0 (>440) or <200 mL/day |

26 * Source: [Vincent et al., 1996](#).

- 27 10) All other adverse and serious adverse events will be recorded as well (see adverse events section to follow).
- 28 11) Change in standard of care inflammatory markers (ferritin, LDH, CRP, D-dimer) where available
- 29 from day 0 to days 7, 14, 21, 28.

1 Exploratory Endpoints:

2 12) Association between antibody levels and donor characteristics/clinical course
3 13) Association between clinical response in recipients and antibody levels in the donors

4

5 **Dosing:**

6 • One dose of 200-300mL (standard collection bag volume) of convalescent plasma will be infused
7 over approximately one hour intravenously with standard vital sign monitoring per unit protocol
8 and standard of care for plasma infusion.

9 • Up to two additional doses of 200 mL of convalescent plasma may be administered within 14 days of initial
10 dose at 1-7 day intervals according to disease severity and tolerance of the infusions. Where possible,
11 plasma from distinct donors will be used for additional doses.

12 • To reduce probability of allergic reaction, pre-medication with diphenhydramine 25mg orally or
13 intravenously will be given within 2 hours before each dose of plasma, unless there is a
14 contraindication noted by treating physician.

15 • Slower infusion time of two hours with optional dose of 20mg intravenous furosemide after first
16 hour can be considered for patients at risk for transfusion-associated circulatory overload

17 • Infusion can be slowed for patient comfort at any time.

18 **Safety:** Patients will be monitored closely during plasma infusion per Inova nursing policy titled
19 “Transfusion/Infusion of Blood Components” Version 01.01. Patients will remain in the hospital for a minimum
20 of 24 hours post-infusion with vital signs performed per standard of care with frequency based on the
21 treating hospital unit. Patients will be discharged from hospital according to standard of care any time
22 after completion of 24 hour observation period post-infusion dosing.

23 If oxygenation worsens post-infusion, treating physician will perform assessment as to the presence of a
24 transfusion related reaction, increase oxygen delivery, and obtain portable chest film if deemed clinically

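### Recipients get one to three infusions, but the primary safety test does not say how repeat infusions count, so the reaction rate can be biased in either direction

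*Combined protocol and SAP*

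**What the plan says.** - **Dosing.** "Up to two additional doses of 200 mL of convalescent plasma may be administered within 14 days of initial" "dose at 1-7 day intervals according to disease severity and tolerance of the infusions". A recipient therefore gets one, two or three infusions, and tolerance is one of two stated grounds for the number. Where possible, "plasma from distinct donors will be used for additional doses".
- **Primary Endpoints, item 2.** The endpoint is "Adverse events related to plasma infusion (within 6 hours of infusion) to include" a list of transfusion reactions. It does not say whether this means the first infusion or every infusion.
- **Statistical Plan, Primary efficacy endpoints, item 2.** "Plasma transfusion related adverse events will be scored as 1+ vs. 0", and the test is a chi-square against expected incidences, "Square test with a hypothesized distribution of expected AE (using the higher incidence estimate". One reference carries a denominator: "Transfusion Associated Circulatory Overload: 1:1,566 to 1:68 plasma units". The references for lung injury, allergic reaction and febrile reaction carry none.
- **Target Recipient Recruitment.** 150 to 200 recipients. No power or precision is given for the safety endpoint.

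Nothing in the Statistical Plan states the unit of analysis for reactions or how second and third infusions enter the count.

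**The concern.** The number of infusions varies between recipients and depends partly on how earlier ones were tolerated. It is therefore tied to the outcome being tested. Two ways of counting are open, and they err in opposite directions.

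- **Per recipient.** A recipient with three infusions has three chances to score, but a per-unit reference describes one chance. An ordinary product can look harmful.
- **Per unit.** If recipients who react tend not to be re-dosed, and susceptibility differs between recipients, later units come mainly from people less prone to react. A real excess can look smaller than it is.

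This is a primary endpoint, so the choice should not be left until the data are in hand.

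**Working it through.** **Inputs from the documents.** References at the upper end of each range: allergic 3%, overload 1/68 = 1.47%. Two-sided 0.05. n = 150 or 200. One to three infusions. The plan states no power figure for this endpoint, so there is none to reproduce.

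**Assumptions, not in the documents.** The 3% allergic figure is treated as per infusion. *c* is the chance that a recipient who has not reacted gets each next infusion. For pooled rates, dosing stops after a reaction. Correlation within recipient is varied.

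**Rejection limit.** The one-sample chi-square against 3% rejects upward at 9 or more reactions of 150 (statistic 4.64; 8 gives 2.81) and at 11 or more of 200 (4.30; 10 gives 2.75). The critical value is 3.84.

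**Counting per recipient, product exactly at the reference, independent infusions.**
- Three infusions each: 1 − 0.97³ = 8.7%. P(X ≥ 9 | 150, 0.0873) = 0.91; P(X ≥ 11 | 200, 0.0873) = 0.97.
- *c* = 0.5: 0.03 + 0.5 × 0.97 × 0.03 + 0.25 × 0.97² × 0.03 = 5.2%. The exact false-flag chance is 0.37 at 150 and 0.46 at 200 (4,000 simulated trials gave 0.37 and 0.44).
- Overload, three infusions each: 1 − (67/68)³ = 4.35% against 1.47%, about threefold. The limits are 6 of 150 and 7 of 200; the false-flag chance is 0.64 and 0.77.

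**Counting per unit, true first-infusion rate 6% (twice the reference).** With *p* the recipient's own risk, the pooled rate is

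E[p + c·p(1−p) + c²·p(1−p)²] / E[1 + c(1−p) + c²(1−p)²].

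If *p* is the same for everyone, this reduces to *p*. If a fixed 6% always react and nobody else ever does, it is 0.06 / (0.06 + 0.94(1 + c + c²)). Intermediate cases use a beta distribution for *p*.

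| Susceptibility | c = 0.25 | c = 0.5 | c = 1 |
|---|---|---|---|
| Equal | 6.0% | 6.0% | 6.0% |
| Correlation 0.2 | 5.7% | 5.4% | 5.0% |
| Correlation 0.5 | 5.3% | 4.6% | 3.7% |
| Fixed subset | 4.6% | 3.5% | 2.1% |

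In the fixed-subset case, *c* = 0.62 gives 0.06/1.944 = 3.1% at 1.94 units per recipient; exactly 3% needs 0.06/0.03 = 2.0 units.

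**Power to flag the doubling, n = 150/200.** First infusion only (exact): 0.55/0.66. Pooled at *c* = 1 (simulated): 0.89/0.95 with equal susceptibility, 0.64/0.72 at correlation 0.2, 0.17/0.21 at 0.5, and essentially zero with a fixed subset.

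**The case against.** A reader might infer that repeats go only to recipients who tolerated earlier infusions, so that pooled rates must be diluted and a product with twice the expected rate will read as normal. The documents do not support that, for four reasons.

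- The dosing text names disease severity as well as tolerance. Neither it nor the Safety section bars a further dose after a reaction.
- The plan does not say that reactions are pooled over units. Its scoring reads more naturally as one score per recipient, where the bias runs upward.
- Selection on tolerance alone dilutes nothing. With equal susceptibility 6% stays 6%, and a doubling reads as normal only near the fixed-subset extreme.
- Using distinct donors where possible weakens carry-over for donor-related reactions, although recipient-related ones such as overload could still cluster.

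These points stand and limit the claim. Two more also stand. The allergic reference has no stated denominator, so the 8.7% comparison rests on reading it as per infusion; the overload comparison needs no such assumption. And the published rates may contain some of the same selection, which the documents cannot settle. None of this tells the analyst how a second or third infusion counts.

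**Conclusion.** The gap is real: the denominator of a primary safety test is undefined while recipients get one to three infusions, partly according to tolerance. The larger and better-supported risk is a false alarm on the per-recipient reading. For allergic reactions it reaches about 91%/97% of trials at 150/200 recipients if everyone gets three independent infusions, and about 37%/46% if each further dose is given with probability 0.5. Clustering of reactions within recipients lowers these figures.

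Dilution under per-unit counting is possible but conditional. It needs reactors to be re-dosed less often and susceptibility to differ between recipients. At a correlation of 0.2 a doubled rate still reads 5.0% to 5.7% against 3%. Full masking is an extreme, not the expected result. Because correlation and number of repeats are unknown, all these sizes are ranges and not predictions.

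**What to change.** State in item 2 of the Statistical Plan that the comparison with the reference incidences uses reactions within 6 hours of each recipient's first infusion, with the number of recipients infused (150 to 200) as denominator. Recipient and unit then coincide, and tolerance cannot affect the count. Alongside, report all second- and third-infusion reactions by infusion number, with the number of recipients not re-dosed because of a reaction.

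The text change is small, but the analysis cost should be stated. The test uses fewer infusions: power to flag a doubling of 3% is about 0.55/0.66 at 150/200 recipients, against about 0.9/0.95 for pooling at full dosing with equal susceptibility and 0.64/0.72 at a correlation of 0.2. For overload, first-infusion power to flag a doubling is only about 0.28/0.37. Later-dose events, overload among them, are shown descriptively and not tested. No change to the dosing rule is proposed.
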